4. Design and Procedures: This will be an unblinded, open-label study enrolling newly diagnosed patients with IPF. We plan to consent 50 subjects including screen fails with a goal of obtaining 30 newly diagnosed individuals with IPF prior to initiation of IPF therapies. 20 subjects will be monitored after the initiation of therapy, 10 subjects will be enrolled that do not start antifibrotic therapy. No subject will be excluded from the study on the basis of gender or ethnicity. IPF is an aging disease with highest incidence in subjects >50 years of age, and therefore subjects will be expected to be >50 years of age. Subjects will be obtained from providers in the Duke Pulmonary Clinics. Informed consent will be

Using Xenon MRI to Evaluate the Efficacy of Therapies for Idiopathic Pulmonary Fibrosis

obtained before a subject begins any study intervention. Subjects will undergo an approximately hour long comprehensive MRI protocol, including administration of multiple doses of HP ^{129}Xe . The subjects will have this initial study prior to initiation of IPF therapies. Then the subjects will have repeat studies at 3, 6 and 12 months following the initiation of therapy. Additional studies including pulmonary function studies, serum for biomarkers, 6 minute walk distance (only at screening visit, 3 month and 6 month visit) and a HRCT (only at the screening visit and 6 month visit) will be performed to determine how ^{129}Xe MRI performs relative to standard of care evaluations for IPF. Finally, following the study visits the research team will prospectively follow the patients' clinical course through periodic reviews of the medical record.

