Incidental Findings – Incidental findings will be handled according to the policies of the Duke IRB. That is, anatomic ^1H MR images will not be routinely reviewed by a radiologist. However, if the technologist or study personnel note suspicious findings in the anatomic (^1H) images at the time of MRI, images from those subjects will be reviewed by a radiologist within 10 business days for incidental findings (tumors, hernias, aneurisms, etc). Such incidental findings will be communicated to the subject's physician. Copies of images will be made available to the subject's physician upon their request. If subjects undergo low-

Using Xenon MRI to Evaluate the Efficacy of Therapies for Idiopathic Pulmonary Fibrosis

dose CT as part of this protocol, those scans will be reviewed for incidental findings by a radiologist on the study team.

11. Costs to the Subject and Compensation: There are no additional costs to the subject for the MRI examination and possible CT scan. Subjects will be compensated \$100.00 for travel/parking and time for each study visit. This does not include the initial screening phone call and the phone call to document initiation of IPF therapy.

12. Data Analysis & Statistical Considerations: All images will be reviewed by the study team. Given that this is an early phase study with no clinical experience this will be a research interpretation and not a clinical read. Images and spectra will be analyzed by a variety of quantitative metrics using established methods. Imaging metrics include the ventilation defect percentage (VDP), percentage of lung with high barrier uptake (Barrier_{high}), and percentage of lung with defects in red blood cell transfer (RBC_{low}). Spectroscopic markers will include the ratio of ¹²⁹Xe transfer to RBCs vs barrier (RBC:barrier) as well as RBC oscillation and frequency oscillation amplitudes. CT scans will be evaluated by a chest radiologist using established criteria to produce a mean fibrosis score based on the extent of reticulation and honeycombing and will range from 0-100%.

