Although sensitivity to therapy response is expected to be highest for the imaging metrics, the study has been conservatively powered on the basis of the spectroscopic RBC:barrier ratio, which thus far, is most well-documented of the ¹²⁹Xe metrics in the literature. Early studies, which did not control carefully for lung inflation reported a variability of 6.6% in this metric. Moreover, a recent study of natural progression in a group of IPF patients (n=18, on a mix of treatments or untreated) revealed a decline in RBC:barrier of 20% in this metric over the course of 6 months. We assume that we will observe a smaller decline in RBC:barrier in our cohort, which will all receive treatment, and estimate that only a 10% decline will be observed at 12 months. Given this estimate of variability and effect size, and requiring 90% power, would be achieved with a sample of only 5 patients. Based on established patterns in our clinics, we expect roughly half the patients to receive pirfenidone with the other half receiving nintedanib. Assuming that one of the drugs reduces RBC:barrier decline to only 5% over 12 months, whereas the other yields a decline of 10%, would require a sample of 19 patients, which is just achievable with the sample of 20 patients expected to be enrolled.

Baseline Repeatability and Prespecified Futility Analysis – As this is a new clinical study with unknown efficacy in detection a preliminary analysis of the data will be performed. Following completion of the first 10 patients in the study the study team will perform an analysis for futility based on test – retest variability. Baseline repeatability of each of the ¹²⁹Xe metrics will be assessed using Bland- Altman plots, and a pairwise, two-tailed *t*-test will be used to check for significant differences. For each derived parameter, the coefficient of variation will be calculated. Our threshold to stop the study is if the RBC:Barrier ratio is outside of 95% CI on test-retest of $\pm 20\%$ of the dynamic range. We estimate the 95% confidence interval to be better than $\pm 10\%$ with this sample size.

Correlation between ¹²⁹Xe metrics, CT scores, and clinical tests will be evaluated using the Pearson correlation coefficient.

To measure changes from baseline, we will calculate the mean, standard deviation, median and range of each metric, and at each time point, the 95% confidence interval for means and averaged changes relative to baseline will be provided. Changes compared to

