Using Xenon MRI to Evaluate the Efficacy of Therapies for Idiopathic Pulmonary Fibrosis

baseline will be tested using the Wilcoxon Singed-Rank test. In all analyses, $P < 0.05$ (two-sided) will be considered the criterion for statistical significance. There will be no adjustment for multiple testing, because of the small number of hypothesis tests considered. The trajectory changes of these endpoints over time will be evaluated using linear models for repeated measures. Point estimates and confidence intervals for relevant parameters will be provided for descriptive purposes.

Baseline images will be analyzed for functional or structural indicators that may predict therapeutic response using mixed linear models. We will conduct this modeling, while considering differences in treatment group, clinical/demographic covariates (fixed effects), and subject (random effect). Diagnostic plots will be obtained to assess possible violations in model assumptions. All statistical analyses and graphics will be generated in R, or similar statistical package.

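### Multiplicity adjustment is waived because the tests are said to be few, but the plan naturally yields 18 xenon change tests with no primary named; the aim of seeing response before FVC also has no direct comparison

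*Combined protocol and SAP*

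**What the plan says.** Section 12 (Data Analysis & Statistical Considerations) sets two-sided P < 0.05 as the criterion in all analyses and adds: "There will be no adjustment for multiple testing, because of the small number of hypothesis tests considered". It gives no count of the tests.

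The same section names three imaging metrics (VDP, Barrier high, RBC low) and, as spectroscopic metrics, RBC:barrier "as well as RBC oscillation and frequency oscillation amplitudes". That makes six. Section 4 sets the imaging visits: "Then the subjects will have repeat studies at 3, 6 and 12 months following the initiation of therapy". For change from baseline, Section 12 summarises every metric by visit, says that "the 95% confidence interval for means and averaged changes relative to baseline will be provided", and then tests changes by Wilcoxon signed-rank.

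Nothing is called primary. RBC:barrier comes closest: "the study has been conservatively powered on the basis of the spectroscopic RBC:barrier ratio", with a 10% decline assumed at 12 months, and it is the only metric in the futility rule. Yet the sentence on powering also says that the imaging metrics are expected to be the most sensitive to therapy response.

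Section 2 gives as an objective the observation of therapeutic response earlier than standard methods, with FVC decline as the example. Section 12 relates xenon metrics to clinical tests only by Pearson correlation.

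**The concern.** Leaving tests unadjusted is defensible in an early-phase study that presents them as exploratory. Section 12 does not give that reason. It applies a significance criterion to all analyses and excuses it by a small test count, which its own list of metrics and visits does not bear out.

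Without a named primary, a single P < 0.05 among these tests is weak evidence. The lead result could also be chosen after the data are seen, most easily from the imaging metrics that the plan expects to perform best. On FVC, a correlation shows association. It does not show that one measure detects change sooner or more sensitively than the other.

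**Working it through.** **The plan's own figures.** Inputs from Section 12: variability 6.6% (used as the SD), two-sided 0.05, 90% power. The one-sample normal formula is n = (SD × (1.960 + 1.282) / δ)².
- δ = 10%: (6.6 × 3.242 / 10)² = 4.58, rounded up to 5. The stated 5 reproduces.
- δ = 5%: (6.6 × 3.242 / 5)² = 18.31, rounded up to 19. The stated 19 reproduces, but from a one-sample formula although the text describes a two-drug comparison.

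Both calculations allow 0.05 for one test on one metric.

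**Test count.** 6 metrics × 3 visits = 18. The Wilcoxon sentence does not itself repeat the visit scope, so the narrowest reading is 6 × 1 = 6. Repeatability t-tests, correlations and the models come on top.

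**Chance of at least one false positive, no true change in any metric.** The documents give no correlations, so these are assumed: 0.5 to 0.9 between visits and 0 to 0.9 between metrics. The three changes share one baseline; with equal independent measurement error, that alone gives a visit correlation of σ²/(2σ²) = 0.5. The figures come from simulation with normal data and n = 20, using the exact two-sided Wilcoxon signed-rank test (critical value 52, attained level 0.0484).

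| Tests | Metric corr. | Visit corr. | Chance |
|---|---|---|---|
| 18 | 0 | 0.5 | 0.547 |
| 18 | 0.3 | 0.5 | 0.513 |
| 18 | 0.5 | 0.7 | 0.415 |
| 18 | 0.8 | 0.7 | 0.299 |
| 18 | 0.9 | 0.9 | 0.187 |
| 6 (one visit) | 0 | – | 0.257 |
| 6 (one visit) | 0.5 | – | 0.207 |
| 6 (one visit) | 0.9 | – | 0.112 |
| 3 (RBC:barrier only) | – | 0.5 | 0.125 |
| 3 (RBC:barrier only) | – | 0.9 | 0.084 |

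**Power of a single named primary** (RBC:barrier, V1 to 12 months, true decline 10%, exact Wilcoxon). With 20 completers, power is above 0.99 at an SD of change of 6.6%, 0.993 at 9.33% (6.6 × √2), 0.91 at 12.5% and 0.89 at 13%. With 15 completers at 12.5% it is about 0.80. Treating 6.6% as an SD of change is an assumption.

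**Between-drug contrast.** Two-sample t-test, 10 per drug, difference 5%, SD 6.6%: power 0.361.

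**FVC comparison.** Let SRM be mean change / SD of change, with decline positive, and ρ the correlation between the two changes. The large-sample variance of SRM₁ − SRM₂ is [2 − 2ρ + (SRM₁² + SRM₂²)/2 − ρ² SRM₁ SRM₂] / n. The 95% half-width at n = 20 is:
- both SRMs 0.3, ρ = 0.8: 1.96 × √(0.432/20) = 0.29 (simulated 0.31);
- both SRMs 0.76 (5/6.6), ρ = 0: 1.96 × √(2.578/20) = 0.70 (simulated 0.75);
- RBC:barrier SRM 10/6.6 = 1.52, FVC SRM 0.3 (assumed), ρ = 0: 1.96 × √(3.193/20) = 0.78 (simulated 0.85);
- RBC:barrier SRM 20/6.6 = 3.03, otherwise the same: 1.96 × √(6.637/20) = 1.13 (simulated about 1.26).

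Simulated coverage of nominal 95% intervals at ρ = 0.5 was 0.914 to 0.920 for the percentile bootstrap and 0.938 to 0.944 for BCa. This is why BCa is preferred.

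**The case against.** The study describes itself as early phase, reports estimates and intervals for description, and supports no regulatory claim. RBC:barrier has a time point, an expected decline, a power target and the only stopping threshold, so an informed reader would probably take it as the lead. Much of this stands. It means that no formal adjustment is required and that the defect is one wrong reason and one missing label. It does not rescue the reason given, and even RBC:barrier alone carries 8% to 13% while no visit is named.

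The count of 18 is an inference from adjoining sentences, which is why the six-test reading is given beside it.

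The high error rates also invite challenge, fairly. Several metrics come from the same barrier and red-cell signals in one session, so zero correlation is unlikely. Section 12 expects decline in RBC:barrier and the greatest sensitivity in the imaging metrics, so it does not expect every metric to stay flat. Nor does it support a scenario in which only RBC:barrier moves.

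On FVC, neither Specific Aim repeats the wish to see response earlier. Per-visit change summaries, if they cover lung function, would bear on it descriptively. What is missing is a direct comparison.

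**Conclusion.** The point holds. The reason for waiving adjustment fails on the plan's own content: 18 tests on the natural reading, six on the narrowest, and no primary among them. Under the assumed correlations and no true change, the chance of at least one false positive is about 19% to 55% for 18 tests and 11% to 26% for six. The upper ends need uncorrelated metrics and no true change in any of them, so they are ceilings rather than forecasts.

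A reader might infer more, and the documents do not support it:
- That the error rate is 1 − 0.95¹⁸ = 60%. This needs independent tests, which changes from a shared baseline are not.
- That a Bonferroni-type correction is obligatory. Naming one primary and calling the rest exploratory is enough.
- That nothing in the plan bears on the FVC objective. Change summaries and correlations do, indirectly; the gap is the absence of a direct comparison, and it is secondary to the multiplicity point.

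The study can run as designed. The change should be made before the data are analysed.

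**What to change.** In Section 12:
1. Delete the reason based on the number of tests.
2. Name one primary test: change in RBC:barrier from V1 to 12 months (V5) in patients who start therapy, Wilcoxon signed-rank, two-sided 0.05. State that it shows change over time, not treatment efficacy.
3. Label every other test exploratory, reported as an estimate with a 95% confidence interval.
4. For the Section 2 objective, add the paired difference in standardised response mean between RBC:barrier and FVC at 3 and 6 months in the same patients, with a BCa bootstrap 95% interval that resamples patients. Describe it as sensitivity to change; it does not establish timing or treatment response.
5. So that FVC is available at those visits, reconcile footnote 3 of the Schedule of Events, under which any one of the lung function tests suffices, with Section 4, which specifies spirometry at V1 and at each follow-up visit.

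**Cost.** A few sentences and a little code, on data already scheduled. The imaging metrics, RBC:barrier at 3 and 6 months, the correlations and the between-drug contrast become exploratory. The plan ties its sample to that contrast (it "would require a sample of 19 patients, which is just achievable with the sample of 20 patients expected to be enrolled"), but at about 36% power little confirmatory value is lost. The primary has about 91% power at an SD of change of 12.5% with 20 completers. Dropout is a real cost, since the chart-review fallback in Section 4 lists no MRI, and 15 completers would leave about 80%. The FVC interval will be wide, with a half-width of about 0.3 to 0.85, and up to about 1.3 if RBC:barrier falls 20% with an SD of 6.6%. It can only describe.
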